#### Parents:

- Parent with child aged 9-11 at participating school participating in the study.
- Able and willing to give informed consent to take part.

#### **Exclusions:**

- Schools that are taking part in an existing air quality study or in a school environment intervention study.
- Participants who are unable to give informed consent due to lack of capacity or if they speak a language that we are unable to facilitate through our resources.

## 3.1.4 Screening for WP7

A shortlist of eligible primary schools will be identified based on local authority NOx exposure data and location in areas of high deprivation. We will approach schools from this shortlist, prioritising those within areas with the highest concentrations of NOx.

Eligible year group/classes of children will be identified through discussions with the recruited schools. It is anticipated that all children within a particular class in each school and their parents will be offered the opportunity to complete the travel survey. This survey will include questions to help us identify:

- i. those participants most interested in changing their travel behaviour and monitoring personal exposure as citizen scientists; and
- ii. those participants who usually walk home from school, who would be eligible to take part in a walk along interview.

The commitment required from teachers, parents and children will be explained to interested schools as part of the recruitment and screening process.

#### **3.1.5 Consent**

**Schools:** Schools will be provided with the head teacher participant information sheet (PIS) (Annex 31) and a school's consent form (Annex 32). Informed consent will be taken from participating schools for the installation of static monitors and NO2 tubes and for the school to facilitate children's use of mobile PM sensors, NO2 diffusion tubes and the EXPOApp3.

**Pupils and parents:** Parents will be given a parent PIS (Annex 33) and a parent consent form (Annex 34). Participating children will also be given a child PIS (Annex 35) and verbal assent will be taken prior to data collection. The parent PIS and consent form will cover the following:

• Consent to take part in three waves of the parent and child travel questionnaire. (The phase 1 questionnaire for parents to complete with their children will be sent home with the PIS.)

- Expression of interest and consent for their child to take part (if eligible and selected) in personal exposure monitoring as a citizen scientist.
- Expression of interest in and consent to take part (if eligible and selected) in a parent and child walk along interviews, and for children to take part in a Photovoice workshop.

**Teachers:** Teachers invited to take part in interviews will be given a teacher PIS (Annex 36) and a teacher consent form (Annex 37).

#### 3.1.6 Withdrawal

All participants will be free to withdraw without giving any reason at any time during the course of the study. Any data collected up to that point will be retained for analysis unless otherwise specified by the participant.

#### 3.1.7 Sample size (Bradford only)

- Schools: 2 schools in areas of high deprivation and high levels of pollution
- Questionnaire: 50 children (25 per school) target sample size, based on inviting a whole class to take part.
- **Personal monitoring**: A sub sample of 20 children will be selected, based on interest in changing and monitoring their travel behaviour.
- Parent/ child dyads: A sub sample of 15 parent child dyads (7-8 per school) will be selected based on children who walk home from school to take part in the walk along interviews.
- **Photovoice discussion groups:** 15 children will be invited to take part in workshops, based on those who took part in walk along interviews.
- **Co-production workshops:** All participants will be invited to take part in a workshop to discuss the findings from the research in their school.

#### 3.1.8 Equipment

- 1) Static air quality sensors
- 2) Portable air quality sensors (Atmotube Pro)
- 3) NO2 diffusion tubes
- 4) Smartphones with ExpoApp3 and Atmotube Pro app
- 5) Tablet (to be provided by researcher on the day for walk along interview) with PicVoice app to allow parent/ child dyads to take photos on their journey.

#### 3.1.9 Data collection

#### 3.1.9.1 Static monitoring

2 static particulate matter monitors (Figure 3) be placed in each of the 2 schools for up to a year, to cover the baseline data collection period, implementation and evaluation of the interventions One monitor will be placed indoors at a key location (for example, classroom) and one will be outside (in playground, close to the classroom). The precise locations may differ between the schools depending on operational considerations. All monitors will measure

particulate matter (PM), temperature (T) and relative humidity (RH), some will additionally measure CO (carbon monoxide), NO (nitrogen monoxide), NO2 (nitrogen dioxide), VOCs (volatile organic carbon) and O3 (ozone).

Figure 3: Optical particle counter (OPC) sensor to measure particulate matter. Produced by (and purchased from) Alaphasense Ltd.

Schools and the research team will be able to access the recorded particulate matter data and (if available) choose to display their data on a public website.

#### 3.1.9.2 Personal Exposure Monitoring

In addition to the static monitors, 3 pieces of equipment will be used to assess personal exposure to the urban exposome on children's journeys to and from schools: portable monitors, NO2 diffusion tubes and smartphones with the ExpoApp3 installed. Children will carry these devices for 1 school week (Monday to Friday). Children will also be given a Citizen Scientist log book that includes information about each device, an incident monitoring sheet and a daily travel diary for completion (Annex 38).

#### Portable monitors

School pupils will be given portable Personal Exposure Monitors (PEM) to wear which will allow quantification of the urban exposome children are exposed to on their journey to and from school. We plan to use the Atmotube PRO wearable device, which children will attach to the outside of a bag provided by the project, using a carabiner clip. This device measures concentrations of particulate matter (PM1, PM2.5, and PM10) and Volatile Organic Compounds (VOCs), plus atmospheric pressure, temperature, and humidity. Children will also be asked to carry a research smartphone with the Atmotube app installed. This smartphone will be carried in a bag provided by the project. Data from the Atmotube Pro will sync with the smartphone app throughout the study week.

Figure 4: Atmotube Pro portable air quality monitor

Care will be taken with data from the PEM monitors to ensure anonymity of the participants. Data taken in, or close to, a child's home will only be displayed without latitude / longitude / school / participant information so as to ensure it is anonymous. This distance will be increased in any instance where this is insufficient to anonymise the data (e.g. houses in remote / easily identifiable locations). Data from within the buffer zone will only be seen by the research team.

#### NO2 diffusion tubes

Children will also be asked to wear an  $NO_2$  diffusion tube during the study week. They should attach this to their outer clothing using a clip supplied with the tube (Figure 5). This will monitor  $NO_2$  concentration.

As  $NO_2$  diffusion tubes do not collect time series data (they only provide an average exposure for the duration of the study week), to estimate  $NO_2$  exposure on children's journeys to/from school,  $NO_2$  readings will also be taken from the school and home environment.

- NO2 tubes will be installed in indoor and outdoor locations in schools ideally the same locations as the static monitors – for the duration of Personal Exposure Monitoring fieldwork.
- Children will be given 2 NO2 tubes to measure exposure at an indoor and outdoor location in their home for the duration of the study week (Figure 6). The tubes and clips/straps will be put in the same bag as the PEM monitor to take home on the 1st day of data collection, along with written instructions on home installation in their Citizen Scientist log book (Annex 38).

Figure 5: NO2 diffusion tube (wearable)

Figure 6: NO2 diffusion tube (static)

#### ExpoApp3

We will provide all children with a research smartphone with the ExpoApp3 installed (Annex 25). The app is designed to measure location and physical activity. Children will be required to carry the smartphones with them throughout the data collection period in a bag provided by the research team. The smartphones will only be enabled with WiFi and GPS functionality and will not have SIM cards that will allow children to make or receive calls. The smartphone will also have the Atmotube app installed; other than this no other apps will be downloaded on the phone. Data from the ExpoApp3 will be sent to the 'ExpoHub' (see Annex 25) when connected to WiFi. No personal data will be displayed on the devices and children will be assigned with a pseudo anonymised identification number.

#### Weekly monitoring routine for children

Children will complete a travel diary on each school day and use the following devices.

Device	1 st Friday	Weekend	Mon-Thurs	2 nd Friday
Atmotube Pro	Wear on journey home from school. Switch off at 7pm, then charge it.	Leave switched off in the kit bag.	Switch on at 7am. Wear on journey to and from school and during school. Switch off at 7pm, charge it.	Switch on at 7am. Wear on journey to school, then hand in to BiB.
Smartphone	Carry home from school in kit bag. Charge it at 7pm.	Leave in the kit bag.	Carry on journey to and from school in the kit bag. Charge it at 7pm.	Carry on journey to school in the kit bag, then hand in to BiB.
Wearable NO 2 tube	Wear on journey home from school. Put it in a safe place in the living room after 7pm.	Leave in the living room.	Wear on journey to and from school and during school. Put it in a safe place in the living room after 7pm.	Wear on journey to school. Close tube and place in kit bag to when told to at school.
Home indoor NO 2 tube	Carry home from school in the kit bag. Place and open as instructed in the living room.	Leave in place.	Leave in place.	Close tube and place in kit bag as instructed to hand into BiB.
Home outdoor NO 2 tube	Carry home from school in the kit bag. Place and	Leave in place.	Leave in place.	Close tube and place in kit bag as instructed to

0	pen as		hand into BiB.
ir	nstructed		
0	outside your		
fı	ront door.		

## Daily monitoring routine for children

Approx.	Location	Actions	Comments
Time			
7.00	In Home	
 
Equipment left in the living room overnight. (Atmotube Pro and Smartphone must be charged.)
 
Unplug Atmotube Pro and Smartphone . Put chargers away in backpack.
 
Switch on Atmotube Pro at 7am.
 
	Atmotube Pro doesn't need to monitor overnight and can be switched off daily between 7pm and 7 am.
	Travel to	Child travels to school as normal,	
	school	
 
carrying the equipment.
 
Atmotube Pro should be clipped to backpack strap.
 
Personal monitoring NO2 diffusion tube should be clipped to coat/outer clothing.
 
	
9.00	Start of the school day	
 
Child carries the equipment with them throughout the school day.
 
Personal monitoring NO2 diffusion tube can be left attached to a coat if the child wears one to school.
 
	
15.30	End of the school day	
 
Class teacher and child checks that they are taking home the:         
 
Smartphone
 
Atmotube Pro
 
NO2 diffusion tube
 
 
 
	If child attends an after school club, equipment should be taken there.
15.30 to 19.00	Travel from school	
 
Child travels home from school as normal, carrying the equipment.
 
Atmotube Pro should be clipped to backpack strap.
 
Personal monitoring NO2 diffusion tube should be clipped to coat/outer clothing.
 
	
19.00	In home	
 
On arrival at home, child places equipment in the living room.
 
Switch off Atmotube Pro at 7pm.
 
Plug in Atmotube Pro and
 
	

37

		Smartphone to charge overnight.	
After school	In home	Child completes a daily travel diary (in Citizen Scientist log book, Annex 38)	This should take no more than 5 minutes each day.

#### 3.1.9.4 School travel questionnaire

Children and their parents will be invited to complete a school travel questionnaire (Annex 39) on three occasions over the course of the project:

- 1. At baseline data collection in Autumn 2021
- 2. During the intervention implementation week in Spring 2022
- 3. At 6 month follow up in Autumn 2022

This child section of the questionnaire will collect data about the children and how they feel about the environment around their home and school, school travel modes and preferences, physical activity, and self-assessed physical and mental health. The parent section of the questionnaire will collect data about the parent, their child's health, reflection on their child's school travel, and support for proposed interventions.

All three waves of the questionnaire will be printed and provided to the children at school. Children can complete their portion of the questionnaire at school or at home depending on the preferences of the teachers and parents. The Parent Information Sheet and Consent From and the Child Participant Information Sheet (Annexes 33, 34, and 35) will be provided at the same time as the first questionnaire. A pre-paid envelope will be included for these documents to be returned directly to the Born in Bradford project office.

#### 3.1.9.5 Walk along interviews

A sub sample of 30 parent and child dyads (15 per site) will be invited to participate in walkalong interviews with a researcher. A researcher will meet the parent and child at school at the end of the school day and accompany them on their journey home. Children and parents will be given a research tablet with the PicVoice app which they will both use to take pictures and record notes of urban exposure on their journey (Figure 6). The app allows users to take pictures and record a voice note to accompany the image.

Further information on this can be found at:

https://play.google.com/store/apps/details?id=com.edukunapps.picvoice&hl=en GB.

The researcher will carry out a semi-structured interview with the parent/ child dyad, following the walk along interview SOP (Annex 40) and aided by an interview guide (Annex 41) and a participant handout (Annex 42). The interviews will be audio recorded for transcription. The researcher will also complete a brief field note diary as soon as possible after the interview (Annex 43). In the event that audio recording of the walk along interview is not possible or poor quality (e.g. due to social distancing), the field note diary will be used to capture additional comments from parents and children that are not recorded by the PicVoice app.

[figure not shown]

Figure 6: Illustration of PicVoice App

#### 3.1.9.6 Photovoice discussion groups

A sub sample of 7-8 children per school (those who take part in the walk along interviews) will be invited to participate in a Photovoice discussion group with a researcher. This will take place on school premises during or after the school day depending on participant preferences. This discussion group will be aided by a discussion guide (Annex 44), and the photos that the children took during their walk along interviews will be used as visual prompts. During the discussion group, children will take part in a mapping exercise, using different coloured stickers to represent unhappy and unsafe places, and safe and favourite places, on their walk to and from school. These discussion groups will be audio recorded and transcribed.

#### 3.1.9.7 Co-production workshop with teachers, parents, and children

A co-production workshop will be held in each school including Year 5 children, teachers, parents, local policymakers, and researchers. This will take place on school premises during or after school hours, depending on participant preferences. The workshops will be aided by an outline of potential activities (Annex 45) using photos taken by children from the walk along interviews and data from the personal monitors. The co-production workshop will use these and discussions to come up with ideas to make the school travel healthier and safer.

#### 3.1.9.8 Focus groups with parents and children

Approximately 6 months after the implementation of the inventions in schools, parents and children will be invited to attend a focus group to discuss their experience of taking part in the project, and the perceived impact and sustainability of the intervention. We will organise 1 or 2 focus groups per school, depending on the number of families who wish to take part. Focus groups will take place on school premises during the school day or after school by arrangement. These focus groups will be aided by a discussion guide (Annex 46) and will be audio recorded and transcribed.

## 3.1.9.9 Teacher interviews

Approximately 6 months after the implementation of the inventions in schools, teachers of pupils in participating classes will be invited to take part in an interview to discuss the school's experience of taking part in the project, and the perceived impact and sustainability of the

intervention. These interviews will take place on school premises during the school day or after school by arrangement. The interviews will be aided by a discussion guide (Annex 47) and will be audio recorded and transcribed.

#### **3.1.10 Analysis**

#### 3.1.10.1 Sensors

The **static sensor data** will be analysed to understand the levels and variability of air pollutants children attending that school are exposed to and identify modifiable sources of exposure.

The **personal exposure** data (PEM data from N=10 children per school) will be used to build a picture of the typical exposure to air pollution that children encounter in their daily life. All visualisations of the data will ensure that the location of the children's homes is not shown. Most map-based analysis will focus on gridded data, which further anonymises it. Through this analysis we aim to identify exposure "hot spots" and clean areas and explore whether different routes would reduce exposure.

#### 3.1.10.2 NO2 diffusion tubes

The  $NO_2$  exposure data will be used to determine the average concentration of compounds that were present in the air: (i) at school; (ii) at the child's home; and (iii) on journeys to and from school over the monitoring period. The results are reported in parts per billion (ppb) and micrograms per meter cubed ( $\mu$ gm-3) to allow comparison with health guideline levels.

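### Average NO2 on school journeys cannot be usefully estimated from the planned week-long tubes, and the tubes' monitoring week is defined in two ways

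*Protocol*

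**What the plan says.** Section 3.1.10.2 of the protocol says that the NO2 data will give average concentrations at school, at the child's home and "iii) on journeys to and from school over the monitoring period", reported in units that allow comparison with health guideline levels.

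The NO2 part of 3.1.9.2 recognises the limit of the method. It says of the tubes that "they only provide an average exposure for the duration of the study week", and that, in order to estimate journey exposure, NO2 "readings will also be taken from the school and home environment". It gives no formula.

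The weekly routine table runs from a first Friday to a second Friday. For the worn tube the first Friday entry is "Wear on journey home from school. Put it in a safe place in the living room after 7pm", and the weekend entry is "Leave in the living room". From Monday to Thursday the tube is worn on both journeys and in school, and goes back to the living room after 7pm. It is closed at school on the second Friday. The daily routine adds that in school the "diffusion tube can be left attached to a coat if the child wears one to school".

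The opening paragraph of 3.1.9.2 defines the week differently: "Children will carry these devices for 1 school week (Monday to Friday").

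**The concern.** The worn tube adds up NO2 over a whole week, of which the journeys are a very small part. To recover a small part from weekly averages, the large parts must be subtracted and the remainder divided by the small time share. That division multiplies every tube error and every mismatch between what a tube measured and what the subtraction needs.

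Section 3.1.9.2 gives school journeys as the purpose of personal monitoring, and monitoring is repeated in all three phases. A journey NO2 figure would therefore naturally be set against guideline levels and compared before and after the interventions. If it is mostly error, neither comparison can be interpreted.

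The two definitions of the week also matter, because the averaging period and the share of living-room time both depend on which one is followed.

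**Working it through.** The protocol states no journey share or tube precision, so there is no figure of its own to reproduce.

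**Inputs from the protocol (weekly and daily routines in 3.1.9.2; 3.1.7)**
- Open time T: Friday 15:30 to the next Friday 09:00 = 7 × 24 − 6.5 = 161.5 h.
- Living-room time: Friday 7pm to Monday 7am (60 h) plus four nights of 12 h (48 h) = 108 h; 108/161.5 = 67%.
- School time Ts: four days of 09:00-15:30 = 4 × 6.5 = 26 h.
- Journeys sampled: 1 + 8 + 1 = 10.
- Children monitored in Bradford: 20.

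**Assumptions, not in the protocol**
- Journey length: 10-30 min, with 5-60 min as a wider range.
- Tube error: SD 1 µg/m3, independent between tubes. Results scale in proportion.

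**Journey share, f = Tj/T**
- 10 min: 1.67/161.5 = 1.03%. 30 min: 5/161.5 = 3.10%.
- 5 min: 0.83/161.5 = 0.5%. 60 min: 10/161.5 = 6.2%.
- Monday to Friday, taken as 102.5 h with 8 journeys or 108 h with 10: 1.3-1.5% at 10 min and 3.9-4.6% at 30 min.

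**Error of the implied subtraction**

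C_journey = (T × C_worn − Th × C_home − Ts × C_school)/Tj, where Th = T − Ts − Tj treats all time outside school and journeys as home time. The error factor is √(T² + Th² + Ts²)/Tj.
- 15 min: Tj = 2.5, Th = 133; √(161.5² + 133² + 26²)/2.5 = 210.8/2.5 = 84.3.
- 30 min: Tj = 5, Th = 130.5; √(161.5² + 130.5² + 26²)/5 = 209.3/5 = 41.9.

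At SD 1 µg/m3 the SD for one child is therefore about 42-84 µg/m3. Dividing by √20 gives 9.4-18.9 µg/m3 for a 20-child mean. The difference between two such single-week means has an SE √2 times larger, about 13-27 µg/m3.

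**Second error model.** Take illustrative levels of 15 (home), 20 (school) and 40 (journey) µg/m3 and a 5% coefficient of variation per tube. For 10-30 min journeys the SE is then 34-100 µg/m3 per child and 7.5-22 for a 20-child mean. At 10% these double, to 67-199 and 15-45.

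**Monday-to-Friday schedule**, with Ts = 5 × 6.5 = 32.5 h and SD 1 µg/m3:
- 102.5 h, 8 journeys of 15 min: √(102.5² + 68² + 32.5²)/2 = 63.6.
- 108 h, 10 journeys of 30 min: √(108² + 70.5² + 32.5²)/5 = 26.6.

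**Bias.** The school tube averages nights and the weekend, whereas the subtraction needs the level in school hours. If the two differ by an illustrative 2 µg/m3, derived journey NO2 shifts by 26 × 2/5 = 10.4 to 26 × 2/2.5 = 20.8 µg/m3, and children at the same school share that shift. A tube hanging on a coat during lessons adds a further mismatch.

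**The case against.** The protocol nowhere states a subtraction. It says that home and school readings will be taken in order to estimate journey exposure, and a formula could be left to an analysis plan. That is fair, and the subtraction is an inference. But the listed devices offer no better route. The portable monitor measures particulates and volatile compounds, and ExpoApp3 gives time and location. A later plan would still have only weekly averages from the worn and home tubes.

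Section 3.1.9.1 says that some static school monitors measure NO2. Where fitted, they could supply school-hours levels and reduce that bias. They touch only the school term. With that term known exactly, the factors become √(161.5² + 133²)/2.5 = 83.7 and √(161.5² + 130.5²)/5 = 41.5, almost unchanged.

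A reader might infer that the output will be pure noise with negative values. The documents do not support that as a certainty, because journey length and tube precision are not given. Counting all of 07:00-09:00 and 15:30-19:00 as travel gives 27.5/161.5 = 17%, and the factor falls to √(161.5² + 108² + 26²)/27.5 = 7.1. For a group mean with long journeys and precise tubes, very imprecise is the fair description. The repeated weeks in 3.1.2 would reduce random error further, but not the bias.

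A reader might also infer that journey exposure as a whole cannot be assessed. It can: 3.1.9.2, 3.1.10.1 and 3.1.10.3 already plan portable-monitor data combined with location. The averages at school and at home do not pass through this division and are not affected in the same way.

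**Conclusion.** The point holds for the third output in 3.1.10.2 only. For 15-30 min journeys, any recovery from weekly averages multiplies tube error roughly 40 to 80 times. It also adds bias that is shared within a school and does not shrink as children are added. The sizes rest on an assumed journey length, an assumed tube SD of 1 µg/m3, independent errors and an inferred subtraction. Following the Monday-to-Friday definition does not rescue the output, since the factor is still about 27-64 for 15-30 min journeys.

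The conflict over the monitoring week is real but separate. It is a wording matter that changes the averaging period from about 102-108 h to 161.5 h, and it adds no weight to the argument about journeys.

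**What to change.** - In 3.1.10.2 and the NO2 part of 3.1.9.2, withdraw journey NO2 as a reported output. Do not compare such a figure with guideline levels, or before and after the interventions.
- Report the worn tube as a weekly personal mean, beside the home and school tube means.
- State that journey-specific conclusions rest on the time-resolved Atmotube particulate data with ExpoApp3 location, as already planned.
- Reconcile the Monday-to-Friday wording in 3.1.9.2 with the Friday-to-Friday table, and use logged tube opening and closing times as the averaging period.

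Two tempting substitutes should not be adopted as they stand. One derives a weekday 7am-7pm mean as (161.5 × worn − 108 × living room)/53.5. It applies a full-week living-room average to nights and the weekend, multiplying any difference by 108/53.5, about 2. It also treats 7am-7pm as all worn, although the daily routine has equipment put down on arrival home. The other caps the worn tube over the weekend. That removes 60 h, leaving 101.5 h open and 48 h in the living room, so the first formula no longer fits, while the home tube still averages the whole week.

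The cost is a few lines of wording and the recording of tube times. No equipment is added. One output is lost that the design could not deliver.
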